During the 12 weeks, if no recordings are made within the hour for 3 consecutive 1-hr prompt windows, RAs will phone participants to inquire about any problems experienced and remind them of the compensation for complying and penalties for non-compliance. Further, if >40% of tests are missed in a week, RAs will phone to remind them that the service will be disconnected (or the \$35 monthly phone service fee forfeited) if they do not submit at least 50% of requested BrAC tests each week. To re-instate service, participants must submit an unprompted breathalyzer test. Phone service will only be reinstated once during weeks 1-12, such that missing >50% of prompts for two weeks during the three month intervention period will result in discontinuation of cell service (or cell phone payments) and BrAC payments throughout the remainder of intervention phase. Individuals who fail to participate in BrAC monitoring will be encouraged to continue with other aspects of study (and non-study) treatment and follow-ups, but they can also decline (see Human Subjects).

Two weeks before the 12-month follow-up, participants will be invited back for a brief re-training on remote BrAC procedures. They will be asked to complete BrACs when prompted for 14 days using similar procedures outlined above (and further detailed below).

Randomization: After completing BL and training, participants will be randomly assigned to a treatment group. A computerized urn randomization program (Stout et al., 1994) will balance participants on AUDIT scores (< or \geq 12), time since last worked for pay (< or \geq 12 months), and gender, variables likely to impact outcomes. Prior to randomizing participants, up to 10 pilot participants will complete a pilot study consent form and study procedures described for Group D below, through month 3 follow-up, for the purpose of monitoring staff on study procedures prior to the randomized trial. Pilot participants may not meet all inclusion or exclusion criteria, with the exception of those relating to safety and loss of benefits.

Group A (n=70; Standard services plus job activity contracting and alcohol monitoring)

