The design includes four treatment groups, allowing for examination of three main contrasts. Aim #1 is to evaluate whether reinforcing negative BrACs reduces drinking. Contrast weights of +1 will be assigned to Groups B and D and weights of -1 to Groups A and C to evaluate differences in LDNS and % negative BrACs in those assigned to interventions reinforcing negative BrACs vs those not. Aim #2 is to assess if reinforcing job-related activities reduces time to job attainment and increases % days working. Contrast weights of +1 will be assigned to Groups C and D and -1 to Groups A and B. Aim #3 is to examine if reinforcing both negative BrACs and job activities produces synergistic effects in terms of primary drinking and employment outcomes. To test this hypothesis, we will assign contrast weights of +2 to Group D, +1 to Groups B and C and -3 to Group A.

Power analyses. Our studies reinforcing drug abstinence find Cohen's d effect sizes of 0.5 to ≥ 1.0 for substance use outcomes ([name] et al., 2000, 2004, 2005abc, 2006b, 2007a, 2010b, 2011a, 2012abc), and our pilot trial using cell phone recorded BrACs yielded an effect size of $d=0.52$ for LDNS and $d=0.62$ for % negative BrACs ([name] & [name], 2013). Our study reinforcing job activities and abstinence (Drebing et al., 2007) had an effect size of 0.47 in terms of increasing job acquisition and 0.49 for abstinence. We conservatively powered this study to detect the smallest of these effect sizes. Using a Type I error rate of $\alpha=.05$, a Type II error rate of $\beta=.20$, and power=0.80 (Cohen, 1988), 62 participants are needed to detect

an effect size of $d=0.47$ between conditions reinforcing a target behavior and conditions not reinforcing that behavior.

We expect a smaller, but still clinically meaningful, effect size of $f=.22$ when comparing across reinforcer conditions. With power 0.80, 64 participants/group can detect $f=.22$ using the 3-group contrast in Aim 3 (Cohen, 1988). To accommodate for missing data, we will randomize 280 participants in total (70/group).

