With 70 participants/group in a 2x2 design, we will be overpowered to detect main effects of reinforcing negative BrACs on alcohol outcomes, and main effects of reinforcing job-related activities on employment outcomes. Nevertheless, this sample size provides power to ascertain if the combined reinforcement intervention is most effective. It also allows detection of a small to medium effect size in determining if reinforcing one behavior can improve both alcohol and employment outcomes (e.g., Group B > A, and Group C > A) to isolate the simplest efficacious reinforcement approach. Moreover, it permits evaluation of secondary outcomes and exploratory analyses of moderators and mediation effects.

Secondary aims are to evaluate the impact of interventions on other drug use, and mental and physical health indices. These are continuous measures, with missing data likely. If no systematic differences in missing data are noted, hierarchical linear models (HLM; Gibbons et al., 1993) using MIXREG (Hedeker, 1993) will analyze differences between groups over time. These analyses have advantages over repeated measures ANOVA as they estimate missing data via model parameter estimates and use real time, rather than scheduled time, of assessments. The same contrasts outlined above will be used to evaluate the aims. Analyses will be conducted for both short-term (e.g., BL to M3, with up to 3 data points/participant: BL,M1,M3) and long-term effects (BL through M12, with up to 6 data points: BL,M1,3,6,9,12). Models will include factors for group (using contrasts above), time, and interaction of group by time. Analyses will ascertain whether the interventions impact areas of functioning beyond alcohol use and employment indices. For example, reinforcement interventions can reduce psychiatric symptoms and improve quality of life ([name] et al., 2007b, in press c).

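### The secondary mixed models leave the group contrast free at the pre-randomisation baseline; a common baseline mean would be a modest, assumption-dependent gain in efficiency

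*Combined protocol and SAP*

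**What the plan says.** The secondary-aims paragraph of the Data Analysis section (combined protocol and SAP) plans hierarchical linear models, fitted with MIXREG, for other drug use and for mental and physical health, provided missing data show no systematic group differences. Baseline is part of the outcome vector in both analyses: "BL to M3, with up to 3 data points/participant: BL,M1,M3" for the short term, and "long-term effects (BL through M12, with up to 6 data points: BL,M1,3,6,9,12" for the long term. On the terms, it says that "Models will include factors for group (using contrasts above), time, and interaction of group by time". One stated advantage is that the models "use real time, rather than scheduled time, of assessments".

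On the order of events, the Randomization paragraph in Methods says: "After completing BL and training, participants will be randomly assigned to a treatment group".

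The opening Data Analysis paragraph allows group differences seen at baseline to be used as covariates. Nothing sets the groups equal at baseline. The secondary-aims paragraph does not state whether time is linear, polynomial or categorical, what the random-effects or correlation structure is, which coefficient is the treatment effect, or what precision or power is expected.

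**The concern.** Because baseline precedes assignment, any group difference there is chance. A model with a free group term spends information estimating a quantity whose expectation is known to be zero. The group-by-time term then behaves like a comparison of change from baseline, which is less efficient than an analysis that adjusts for baseline.

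A second issue depends on how time is coded. If time is one straight line and an effect appears early and then holds, the fitted line does not start at zero: the free group term takes part of the effect and the slope carries the rest. If the slope alone were reported as the treatment effect, it would be too small.

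At stake are interval width and power for the secondary outcomes. The four primary outcomes use ANOVA or ANCOVA and Cox models and are not affected.

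**Working it through.** The plan gives no precision figure for these models, so there is nothing to reproduce. The check compares the planned model with a baseline-constrained one.

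**Inputs from the document.** Visits at 0, 1 and 3 months, or 0, 1, 3, 6, 9 and 12; 70 per group; for Aim 1, "Contrast weights of +1 will be assigned to Groups B and D and weights of -1 to Groups A and C", so 140 against 140.

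**Assumptions, not in the document.** Outcome SD 1, complete data, and compound symmetry with correlation ρ, taken as 0.5 to 0.7 and then varied.

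**1. Linear time, short term.** Let V be the within-person covariance and t = (0, 1, 3). Write a = 1′V⁻¹1, b = 1′V⁻¹t, c = t′V⁻¹t. The slope-difference variance is proportional to a/(ac − b²) with a free group term and to 1/c under a common baseline. The fractional cut is b²/(ac).

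- ρ = 0.5: a = 1.5, b = 2, c = 12. Cut = 4/18 = 22.2%.
- ρ = 0.7: a = 1.25, b = 1.667, c = 17.78. Cut = 2.778/22.22 = 12.5%.

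The SE of the 3-month effect is 3 × √(variance × 2/140). At ρ = 0.5 it goes from 3√(0.1071 × 2/140) = 0.117 to 3√(0.0833 × 2/140) = 0.104, which is 11.8% smaller. At ρ = 0.7 it goes from 0.091 to 0.085, which is 6.5% smaller.

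**2. Categorical time, Month 3 effect.** The variance is proportional to 2(1 − ρ) when free and 1 − ρ² when constrained, a cut of 1 − (1 + ρ)/2. That is 25% at ρ = 0.5 (1.00 to 0.75) and 15% at ρ = 0.7 (0.60 to 0.51). The SE is 13.4% and 7.8% smaller.

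**3. Sensitivity of the variance cut, linear time.**

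| Structure | Cut |
|---|---|
| Short term, ρ = 0.3 / 0.4 / 0.6 | 33% / 28% / 17% |
| Short term, ρ = 0.8 / 0.9 | 8% / 4% |
| Short term, random slopes added, ρ = 0.5 to 0.7 | 7 to 27% |
| Short term, AR(1), monthly correlation 0.5 / 0.7 | 45% / 33% |
| Short term, ρ = 0.5, 20% missing per follow-up visit | 21% |
| Long term, compound symmetry, ρ = 0.5 / 0.7 | 17% / 9% |

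**4. Early, sustained effect under a straight line.** Let the true difference be 0 at baseline and d at every later visit. Under compound symmetry, the free fit to the group difference is the ordinary least-squares line.

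- Short term: slope = (4/3)/(14/3) = 0.286 per month, so 0.86d over 3 months. The group term is 0.29d, and the fitted Month 3 difference is 0.29d + 0.86d = 1.14d.
- Long term: slope = 5.167/110.83 = 0.0466 per month, so 0.56d over 12 months. The group term is 0.59d, and the fitted Month 12 difference is 1.15d.

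If the true effect grows linearly, the group term is zero and nothing is lost. With categorical time the group term is the baseline difference alone, so none of the effect moves.

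**5. Does dropping the group term repair step 4?** Not reliably. With time still linear, the constrained 12-month effect is 0.80d at ρ = 0.5, 0.68d at ρ = 0.7, and about 1.3d under AR(1) with monthly correlation 0.5 to 0.7.

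**The case against.** The strongest reply is that group, time and group by time with baseline as an outcome is a valid analysis. A free baseline contrast does not bias a correctly specified interaction, and the paragraph promises no power that could be missed. This stands, and it keeps the point at the level of efficiency.

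Three stronger readings are tempting, and the documents do not support them:

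- A reader might take 12 to 22% as a property of the plan. It needs linear time, a random intercept and correlation 0.5 to 0.7, none of which is stated. It is also a variance figure, larger than the change in interval width.
- A reader might infer that the group term absorbs an early benefit however time is coded. That needs a straight line together with a non-linear effect. Using real assessment times suggests continuous time but does not fix its form; in this section a linear form is written only for the latent growth models, which also allow a quadratic.
- A reader might infer that the planned model understates the treatment effect. Step 4 shows that its fitted Month 3 difference, at 1.14d, is above d. The shortfall arises only if the slope alone is reported, and the plan does not name the slope as the effect.

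Using observed baseline differences as covariates is a partial counter-argument, but it does not impose a common baseline mean.

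**Conclusion.** The point holds as a modest efficiency improvement for the secondary outcomes. Under compound symmetry with correlation 0.5 to 0.7, a common baseline mean would cut the variance of the short-term treatment contrast by about 12 to 22% with linear time or 15 to 25% with categorical time, and the SE by about 6 to 13%. With linear time the variance cut runs from about 4% to 33% over correlations 0.9 to 0.3, and is larger under AR(1) at the same monthly correlation. The direction follows from randomisation after baseline; the size depends on a correlation the documents do not give.

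The straight-line problem is separate and conditional. For an effect complete by Month 1 and then sustained, under compound symmetry, the slope alone gives 0.86d at Month 3 and 0.56d at Month 12. It comes from the form of time, and dropping the group term does not cure it.

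**What to change.** In the secondary-aims paragraph of Data Analysis, for both the short-term and long-term models, state that:

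1. group means are constrained equal at the pre-randomisation baseline, with the group main effect omitted;
2. time enters as categorical visit, or another form able to follow a plateau (for example piecewise in real time), not as a single straight line;
3. each aim is tested by its contrast-by-time terms at named time points, such as Month 3 and Month 12.

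This takes a few sentences and no new data. The costs are small but real. For one contrast, the fixed effects rise from 4 (intercept, contrast, time, product) to 5 in the short-term model (1 + 2 + 2) and 11 in the long-term model (1 + 5 + 5). Visit coding makes less use of exact assessment dates.

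If the effect really did grow linearly to Month 12, a constrained Month 12 visit contrast would be less precise than the planned slope. In the variance units of step 2, it is 1 − ρ² against 144(1 − ρ)/110.83: 0.75 against 0.65 at ρ = 0.5, and 0.51 against 0.39 at ρ = 0.7. A piecewise form in real time is a reasonable compromise if exact dates matter.

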Additionally, this study will estimate the costs and cost-effectiveness of the reinforcement interventions relative to usual care. If they increase the proportion of individuals who transition to re-employment and reduce time to job attainment, reinforcement interventions may be cost-effective and ultimately integrated in the context of unemployment services. Importantly, reinforcement interventions are now being applied nationwide in the context of substance abuse treatment services ([name] et al., in press b) as well as in other health care arenas (National Business Group on Health, 2013). These dissemination experiences bode well for their ultimate adoption in the context of unemployment services, if benefits are found in this study.

Significance

The unemployment rate in the US remains 7.7% (Bureau of Labor Statistics, 2013), and this rate disguises a larger change in employment patterns, in which precarious or impermanent jobs, that encompass a triad of contingent duration of employment, absence of benefits, and reduced compensation, are increasing (Kalleberg et al., 2000). In part because of this trend, our nation is experiencing the highest poverty level since the early 1980s (Danziger et al., 2012), with a 45% increase in food stamp program enrollment between 2009 and 2012 (Tavernise, 2012). Health disparity groups, including racial/ethnic minorities and those with substance use problems, are most impacted by job loss and unemployment.

Recent data from the National Survey on Drug Use and Health (SAMHSA, 2011) indicate that 33.2% of the unemployed binge drink, and 14.8% have an alcohol use disorder, nearly double the rate of employed persons. The loss of a job, especially involuntary job loss, results in substantial financial, family, and personal stress, along with an increase in unstructured time, all of which can impact alcohol use (Forcier, 1988). Most cross-sectional studies have found greater frequency of hazardous drinking in unemployed versus employed samples (Bolton & Rodriguez, 2009; Dooley & Praise, 1998; Khalt et al., 2004; Mulia, et al., 2013). Longitudinal studies likewise demonstrate that loss of employment can result in greater alcohol consumption and problems (Catalano et al., 1993; Claussen, 1999; Davalos et al., 2012; Mossakowski, 2008; Popovici & French, 2013; Thomas et al., 2005), particularly among men (Virtanen et al., 2008; Deb et al., 2011) and individuals with lower educational attainment (Deb et al.,

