Timeline: Months 1-3 will be used for training, start-up efforts and pilots. We expect to randomize about 7-8 participants into the study each month in months 4-42. This rate of recruitment is feasible because over 500 unique clients receive services each month at CTULA, with an estimated 15-20% meeting all inclusion criteria (and $<15\%$ are expected to meet exclusion criteria). Given the number of clients served throughout this agency, we plan to limit recruitment to one or two of the employment agency sites, but can expand to other sites if needed. Recruiting more quickly would necessitate more study staff due to the number of intervention visits, and this rate is consistent with our substance abuse treatment studies. With this enrollment rate, all intervention should be completed by month 47 and final follow-ups by month 55, leaving 5 months for analyses and report writing.

Data Analysis: An important issue preceding analyses is to identify baseline differences between groups despite random assignment. Group differences that may relate to outcomes (e.g., psychiatric diagnoses, occupational or medical status, drinking severity, services received) will be used as covariates or fixed factors in analyses. All randomized participants will be included using intent-to-treat analyses. Four primary outcomes are determined a priori: longest duration of negative samples (LDNS), % negative BrACs, % days worked for pay, and time to job attainment. The first three are continuous variables that can be transformed if needed. Drinking outcomes rely primarily on objective indices (BrACs), with subjective reports supplementing objective indices, such that one can be considered drinking if either index is positive. For LDNS, missing BrACs will be considered to break a string of negative samples. For % negative BrACs and % days working, missing data will be considered missing (not impacting the denominator) in one analysis, and positive/not working in another to consider the range of possibilities. ANOVAs (or ANCOVAs) will be conducted for drinking data and % days employed, evaluating both short-term (BL to month 3) and longer-term (throughout follow-up) efficacy. Time to job attainment will be evaluated with Cox survivor analyses, including covariates if needed.

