Economic Evaluation. If primary aims are supported, we will conduct cost-effectiveness analyses.

These interventions can be costly, and not only must costs of reinforcers be included, but so must administration costs, which include staff time for managing and delivering reinforcers. Despite costs, these interventions may provide benefits to society in terms of increased productivity and reduced healthcare service utilization (hospitalizations, ER visits). This study will estimate costs of these reinforcement interventions and determine their net benefit in terms of improving both drinking and employment outcomes.

a. Comprehensive administrative costs of interventions will be quantified (Olmstead et al, 2007abc; Rosenheck et al, 1995; Sindelar et al. 2007ab), including costs of prizes, mileage for purchasing them, BrAC testing and management (personnel time to arrange and review videos, and cell phones costs in Groups B and D), and setting and verifying job-related activities (Groups C and D only). Costs related exclusively to data collection will not be included (i.e., cell phones and staff salary for collection and viewing BrAC videos when not reinforced in Groups A and C). Costs for usual employment and clinical services, and reimbursement for same when applicable, will be ascertained.

b. General healthcare costs will be estimated by multiplying service units used by average unit costs. In- and out-patient, day hospital, aftercare and emergency room services will be estimated from CT claims data, and nationally from the Market Scan database, which estimates service costs.

c. Societal costs will be obtained on productivity (days worked, earnings, and workdays affected by substance use), automobile crashes (including property damage, injuries, and fatalities), and criminal justice system costs. Participants receiving reinforcement interventions may have reduced societal costs, and the SU collects data on these variables, police contacts, court hearings, and incarceration, along with timing of events that resulted in criminal justice service use so acts occurring before study participation can be separated from those occurring during it in terms of resource utilization. Unit costs of services will be estimated from national reports (Pastore & Maguire, 2003; US Dept. of Justice 2006).

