Net benefits. Resource utilization and cost data will be used to estimate mean net benefit (benefits – costs) per patient in each group from agency and societal perspectives (Drummond et al, 2005; Zarkin et al., 2008). Mean net benefits, and confidence intervals around estimates, then will be calculated by subtracting mean net benefit of reinforcement conditions from standard care. Finally, sensitivity analyses (Olmstead et al., 2007a; Drummond et al., 2005) will determine the robustness of the net benefit to alternative assumptions about a variety of cost parameters (e.g., unit costs of services, reimbursements received).

Cost-effectiveness ratios. If the interventions engender net benefits (as they have been shown to in the context of substance abuse treatment; Lott & Jencius, 2009), then they ought to be adopted. Even in the absence of a net benefit, the incremental cost-effectiveness ratio (ICER) is critical to policy decisions. The ICER is calculated as: (i) incremental costs to (ii) incremental effectiveness (difference between average effectiveness of treatments in terms of days abstinent or employed). Using expert panel recommendations (Gold, 1996; Johannesson, 1996; Weinstein, 1996), we will present traditional ICERs and uncertainty of the ratios (Gold, 1996; O'Brien et al., 1994) and derive a single synthetic measure of multiple indicators of effectiveness, including quality of life (Hargreaves et al., 1997; Rosenheck et al., 1998). We will also conduct acceptability curve analysis to provide policy relevant interpretations (Fenwick et al, 2001,2004; Lothgren & Zethraeus, 2000; Polsky et al., 1997; vanHout et al., 1994). Multiple samples are selected randomly (bootstrapped), with replacement, from the original sample to approximate the larger population. Incremental cost and effectiveness values and ICERs can be calculated for each new sample and compared with theoretical "willingness to pay" values for an outcome, such as days without drinking or days employed. Such analyses inform policy makers in decision-making (Olmstead et al, 2007ab; Sindelar et al, 2007b) and can be conducted with samples even smaller than those herein (Olmstead et al., 2007c,2009; Sindelar et al., 2007a).

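### The cost-effectiveness analysis is conditional on the primary aims being supported, which conflicts with the unconditional aim and leaves the condition undefined

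*Combined protocol and SAP*

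**What the plan says.** The last paragraph of Specific aims, after the three numbered primary aims, states: "Additionally, this study will estimate the costs and cost-effectiveness of the reinforcement interventions relative to usual care". Nothing there makes the analysis depend on the trial's results. Preliminary studies also says, without condition, that intervention costs and benefits from individual and societal perspectives will be estimated.

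Economic Evaluation begins: "If primary aims are supported, we will conduct cost-effectiveness analyses". The paragraph that follows returns to unconditional wording: "This study will estimate costs of these reinforcement interventions and determine their net benefit in terms of improving both drinking and employment outcomes". The Net benefits paragraph then sets out net benefit with confidence intervals. The Cost-effectiveness ratios paragraph sets out ICERs, bootstrap resampling and acceptability curves, and remarks: "Even in the absence of a net benefit, the incremental cost-effectiveness ratio (ICER) is critical to policy decisions".

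The aims to be supported are tested under Data Analysis: "Four primary outcomes are determined a priori: longest duration of negative samples (LDNS), % negative BrACs, % days worked for pay", plus time to job attainment. Future directions describes what would follow if job reinforcement raised employment without reducing drinking, and if alcohol reinforcement did the reverse.

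**The concern.** One part of the document promises an economic answer and another makes it depend on how the primary tests turn out. An analyst who follows Economic Evaluation literally would leave a stated aim unanswered after a negative or mixed trial.

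The condition also has no rule for applying it. The plan does not say whether one aim, two or all three must be supported, on which outcomes, over which period (to Month 3 or through follow-up), or under which of the two missing-data rules. Whether the condition is met could therefore be decided after the results are known.

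Finally, if the condition amounts to a significance test, an ICER appears only when the effect estimate happens to be large enough. That selects for favourable estimates.

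**Working it through.** **1. The statements side by side.**
- Specific aims: cost-effectiveness, unconditional.
- Preliminary studies: costs and benefits, unconditional.
- Economic Evaluation, first sentence: cost-effectiveness, conditional.
- Economic Evaluation, next paragraph: costs and net benefit, unconditional wording, but under the conditional opening.

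The first and third cannot both be followed if the aims are not supported. The fourth leaves open how far the condition reaches.

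**2. Can the condition be applied?** It would have to be read across three aims, four primary outcomes, two time windows, and two missing-data rules for % negative BrACs and % days working. No combination is named. The mixed outcomes in Future directions have no assigned consequence.

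**3. The plan's own figure.** The plan gives no power figure for the economic analysis. The only one for the main effects is 62 participants for d = 0.47 at α = .05 and power 0.80. It does not reproduce: n = 2(1.960 + 0.842)²/0.47² = 71.1, so 72 per condition two-sided (56 one-sided). This does not affect the present point, because with 70 per group each main effect compares 140 with 140.

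**4. What the condition would do if *supported* meant significant.** This reading is an assumption. Inputs: 140 per side (Power analyses); d = 0.47 (Power analyses); d = 0.30 and 0.20 (assumed, not in the documents); two-sided .05 (sidedness is not stated).

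- SE = √(2/140) = 0.1195 and μ = d/SE.
- Chance of significance: p = Φ(μ − 1.96).
- Mean reported effect ÷ true effect, given significance: 1 + φ(1.96 − μ)/(p·μ).
- Median ICER ÷ true ICER, incremental cost held fixed: μ/[μ + Φ⁻¹(1 − p/2)].

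For d = 0.47: μ = 3.932, p = 0.976, ratio = 1 + 0.0571/(0.976 × 3.932) = 1.015.

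| True d | p, one main effect | Mean reported ÷ true effect | Median ICER ÷ true | Both Aims 1 and 2 significant | No ICER reported |
|---|---|---|---|---|---|
| 0.47 | 0.976 | 1.015 | 0.99 | 0.95 | 5% |
| 0.30 | 0.709 | 1.19 | 0.87 | 0.50 | 50% |
| 0.20 | 0.387 | 1.59 | 0.66 | 0.15 | 85% |

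The last two columns take the condition to require significance on both Aim 1 and Aim 2, with additive effects and independent alcohol and employment errors, so the joint probability is close to p² (0.976² = 0.95). A simulation of the 2×2 design with 400,000 replicates agreed. It gave the same mean inflation for Group D against Group A.

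**5. Sensitivity.**
- The ICER denominator is the difference in days abstinent or employed, which is related to the primary outcomes but not identical. If its estimate correlates ρ with the tested one and has the same standardized effect, the ratio becomes 1 + ρ(m − 1), where m is the mean ratio in the table. At d = 0.30 and ρ = 0.5 to 0.7, inflation falls from 19% to about 10–13%.
- If the condition were a 70 vs 70 comparison with standard care, inflation at d = 0.47 would be about 13%.
- At d = 0.47 (140 vs 140, cost fixed) the mean ICER, unlike the median, is about 5% above the true value, because a ratio is convex in its denominator.

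**The case against.** Five points can be made for the plan as written.

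- **The plan says *supported*, not *significant*, and at its own planning effect the selection is negligible.** Both are correct. The other planning effects quoted (0.49, 0.52, 0.62) are larger still. Against that, 0.47 comes from a trial that reinforced both behaviours together, over 16 weeks and in a different population, so a smaller effect for a single target cannot be excluded. The documents give no value for it.
- **The modelled ICER shift holds incremental cost fixed.** This stands. Prizes are earned for each negative test and each completed activity, and prize cost is counted, so a chance-high response would tend to raise cost too and offset part of the shift.
- **The condition does not change any calculation within this trial.** Also correct. The inflation is a property of reporting selectively across possible trials.
- **The remark "Even in the absence of a net benefit, the incremental cost-effectiveness ratio (ICER) is critical to policy decisions" does not contradict the condition.** A reader might take it as a second contradiction, but the documents do not support that. No net benefit means that benefits do not exceed costs, and this can happen when the primary aims are met.
- **Costs may still be reported.** A reader might infer that a failed aim leaves no cost answer at all. The sentence "This study will estimate costs of these reinforcement interventions and determine their net benefit in terms of improving both drinking and employment outcomes" carries no condition, so costs and net benefit are arguably outside it.

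None of this removes the conflict between Specific aims and Economic Evaluation, or supplies a definition of *supported*. The Specific aims paragraph does go on to say the interventions may be cost-effective if they improve employment, but that qualifies the conclusion and not whether the analysis is done.

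**Conclusion.** The concern holds as an internal conflict with an undefined condition. Read literally, the plan can leave a stated aim without its ICER and acceptability curve after a negative or mixed result. If the condition means significance on both Aims 1 and 2, that would happen in about 5% of trials at d = 0.47, 50% at an assumed 0.30 and 85% at an assumed 0.20, given additive effects and independent errors.

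Selection bias is a secondary point. If *supported* means significant, effects reported with an ICER tend to be inflated by about 1.5% at the planned d = 0.47 (140 vs 140), 19% at 0.30 and 59% at 0.20, and by less to the extent that the ICER outcome differs from the tested one. A reader might go further and conclude that the plan's ICER will understate cost per unit gained by about a third. That figure needs d = 0.20, which is not in the documents, a significance rule that the plan does not state, an ICER outcome identical to the tested outcome, and fixed prize cost. The documents do not support it as a finding.

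**What to change.** Delete the conditional opening of Economic Evaluation so that it agrees with Specific aims. State that costs, net benefit, ICERs and acceptability curves will be reported for all randomized participants, by group, whatever the primary results, with the bootstrap uncertainty already planned.

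The cost is some analyst time and the extraction of unit costs from the claims, database and national sources that the section names. No further participant data are needed: the service-use form is scheduled at baseline and Months 1, 3, 6, 9 and 12 in all groups, and draws and prizes are logged under Data Quality Control.
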